### 17.1.2 Deaths and Serious Adverse Events

A listing of deaths and a listing of SAEs will be provided by subject.

### 17.1.3 Laboratory Data

Clinical laboratory data will be presented using units from the study data tabulation model (SDTM) Controlled Terminology.

A descriptive statistics summary of continuous laboratory results and derived changes from baseline for cardiac markers, chemistry, coagulation, hematology, and urinalysis will be provided by cohort and scheduled timepoint.

Laboratory abnormalities outside of the normal laboratory reference ranges and associated grades (according to study specific DMID criteria specified in the 2014 DMID Adult Toxicity Grading Scale in Appendix 5) should be denoted where possible. For those analyte results that are out of the normal range and do not have an established DMID toxicity criteria, the severity grading will be provided by the PI. The number and percentage of subjects experiencing treatment-emergent graded toxicities will be summarized.

A shift table describing the change in continuous clinical laboratory values from baseline to follow-up (number and percentage of subjects) will also be provided. The following categories will be used: Normal, DMID Grade 1, DMID Grade 2, DMID Grade 3, DMID Grade 4.

All laboratory data will be listed by subject, including laboratory variables not listed in the protocol.

A separate listing of out-of-range values will also be provided. Normal ranges will be used directly from the clinical laboratory and will be included in the listings for reference. Flags for high and low values will be provided in the listings.

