### 3.0 Introduction

This Statistical Analysis Plan (SAP) describes the statistical methods that will be used during the analysis and reporting of data collected under BioCryst Pharmaceuticals, Inc., Protocol BCX4430-106.

This SAP should be read in conjunction with the study protocol and electronic case report form (eCRF). This version of the SAP has been developed using the protocol dated 11-Jan-2019 and the final eCRF(s) dated 30-Oct-2018.

An approved and signed SAP is a requirement for database lock.

This SAP covers all results that will be processed by the PRA Early Development Services (EDS) Biostatistics Department.

PRA EDS will perform the final pharmacokinetic (PK) and safety and tolerability analyses.

This SAP supersedes the statistical considerations identified in the protocol; where considerations are substantially different, they are identified. Any post-hoc or unplanned analyses, or substantive changes from the planned analysis in this SAP performed to provide results for inclusion in the clinical study report (CSR), will be clearly identified in the CSR. Changes to planned analyses do not require an updated SAP but should be denoted in the CSR if significant.

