## 7.0 Overview of Planned Analysis

### 7.1 Changes from Protocol

There are no changes from the protocol.

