### 9.2 Analysis Data Definitions

#### 9.2.1 Baseline Definition

Unless otherwise stated, baseline for post dose evaluations is defined as the last observation recorded before the first study drug administration for each regimen as indicated in Appendix 2 (Schedule of Assessments). The last observation can be an unscheduled/repeated measurement. Baseline ECGs will

be calculated from an average of the triplicate readings prior to initiation of treatment on Day 1 of each treatment period.

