**9.5 TFL Layout**

Report layout will be according to the PRA EDS standards, which are International Council for Harmonisation (ICH) E3 compliant. The layout of TFLs will be according to the PRA EDS standards.

TFL shells are provided with and approved as part of this SAP. Small changes to shell layout due to the nature of the data may be required after database lock at the discretion of the PRA project statistician. Other changes to the shells may be out of scope. The TFLs will be provided both individually in revisable text format (RTF) format, with separate files for each table, figure, and listing, and combined in Adobe PDF format. All TFLs will be in letter format.

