- b. A physical examination consisting of the head and neck, skin, chest (lungs and heart), abdomen (gastrointestinal tract, liver, spleen and kidneys), back, musculoskeletal system, and neurologic system should be conducted at screening and on Day 4 prior to discharge. Breast and genitourinary system do not require examination unless the potential subject indicates a complaint or comorbidity that could result in exclusion. All other physical exams will be symptom directed. The site of infusion should be checked for any changes in skin.
- c. Three (3) serial ECGs will be performed at screening and baseline 1–3 minutes apart. Pre-dose ECG should be collected within  $\leq 2$  hours of the first dose.
- d. 12-lead ECGs will be conducted on Day 1 at 2 and 4 hours post dose (post start of the infusion) and on Day 2 at 24 hours post dose. An acceptable window is  $\pm 10$  minutes from the nominal time point. All subsequent ECGs are daily.
- e. Cardiac telemetry will be initiated  $\geq 2$  hours prior to administration of the dose and will continue for 24 hours after the infusion is started. Subjects may be disconnected for bathroom, hygiene needs, and for 20-minute periods 3 times a day for meals. In addition, subjects may be disconnected for 10 minutes every 2 hours while awake for mild physical exercise such as walking or calf exercises.
- f. The ECHO may be performed at any time from screening to Day -1 for eligibility determination. An ECHO should also be performed on Day 3. An acceptable window for the Day 3 ECHO is up until Day 4 discharge.
- g. Vital signs (except temperature) will be obtained pre-dose (within 2 hours of dosing) 1, 2, 4, and 8 hours post dose (post start of the infusion) on Day 1, at 24 hours post dose on Day 2 and once per day where indicated. Oral temperature will be obtained at 8 hours post dose on Day 1 and at 24 hours post dose on Day 2. Subjects should be rested for 10 minutes in the supine position prior to vital sign measurements.
- h. A serum pregnancy test will be administered at screening to all women; all other pregnancy tests performed during the study may be urine pregnancy tests.
- i. An FSH level will be measured in women who report that they have been postmenopausal  $\leq 2$  years.
- j. Free testosterone will be measured in male subjects.

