- k. Plasma for PK galidesivir analysis will be collected pre-dose, 30 min (halfway through the infusion), 1 h (end of the infusion), 1.25 h, 1.5 h, 2 h, 3 h, 4 h, 6 h, 8 h, 10 h, 12 h, 16 h, 24 h, 36 h, 48 h, 60 h, 72 h, and 96 h following the start of the infusion. The pre-dose PK sample must be collected within  $\leq 1$  hour of the dose. Assessment windows around each PK draw will be  $\pm 2$  minutes for sampling times up to 2-hour post dose and from 2-hour post dose onward,  $\pm 10$  minutes while subject is confined in the unit. All sample times are from the start of the infusion.
- l. For the analysis of urinary excretion of galidesivir, an aliquot of urine will be collected pre-dose (0 hour) and all urine will be collected for the following post dose intervals: 0–12 hours, 12–24 hours, 24–48 hours, 48–72 hours, and 72–96 hours. All sample times are from the start of the infusion.
- m. Baseline for study post dose comparisons. NGAL, cystatin C, UACR, testosterone, troponin I, and CK-MB can be collected on Day -1 or Day 1 (pre-dose).
- n. Subjects will return to the CRU to have a plasma PK sample collected on Day 5 (+1), Day 7 (+1), and Day 14 ( $\pm 1$ ). This visit is intended to be a short visit (approximately 1-2 hours) and can take place at any time during the specified window. A plasma PK sample will also be collected at the follow-up visit on Day 21.

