## Appendix 4: Shells for Post-Text Tables, Figures and Listings

Shells are provided in a separate document.

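### SAP 7.1 declares no changes from the protocol, yet the SAP's laboratory plan departs from it on schedule, marker grading and treatment grouping without saying so

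*SAP*

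**What the plan says.** SAP 3.0 sets the standard: "This SAP supersedes the statistical considerations identified in the protocol; where considerations are substantially different, they are identified". SAP 7.1 then reports: "There are no changes from the protocol".

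**Schedule.** Protocol 7.1 and Table 5 have discharge on Day 5, at 96 hours, and return visits on Days 6, 8 and 14. SAP Appendix 2, presented as the protocol's schedule, has discharge on Day 4. Footnote f reads "An acceptable window for the Day 3 ECHO is up until Day 4 discharge", and footnote n reads "Subjects will return to the CRU to have a plasma PK sample collected on Day 5 (+1), Day 7 (+1), and Day 14".

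**Markers.** Protocol 11.3.1.7 leaves the analysis of cystatin C, NGAL, testosterone, CK-MB, troponin and UACR to the SAP. It outlines change from baseline and, where applicable, grading of out-of-range values as multiples of the normal limit. SAP 17.1.3 has no such rule. Analytes without DMID criteria are graded by the PI.

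**Grouping.** Protocol 12.3.1.3 wants laboratory results for each cohort by visit and treatment assignment, and graded toxicities and shifts by treatment group. SAP 17.1.3 provides descriptive summaries "for cardiac markers, chemistry, coagulation, hematology, and urinalysis will be provided by cohort and scheduled timepoint" and gives no grouping for toxicities or shifts.

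**The concern.** Laboratory abnormalities are part of the primary endpoint. Protocol 4.5 names the kidneys as the principal target organ in rats and monkeys after IV infusion and adds NGAL and cystatin C for that reason. Testosterone is monitored in men, and the testes were among the organs affected in rats. These tables are therefore where a drug effect on the target organs would be expected to show.

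The SAP takes precedence over the protocol's statistics and promises to flag substantial differences. With none flagged, a programmer or reader cannot tell an intended departure from a copying error. Three things are at stake: whether every scheduled draw reaches a by-timepoint summary, whether the organ markers are graded by a rule fixed in advance, and whether the laboratory tables are laid out by treatment as the protocol requires.

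**Working it through.** The plan gives no figure to reproduce. The check sets the texts side by side and counts marked cells.

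**1. Schedule (protocol Table 5; SAP Appendix 2)**

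| Item | Protocol | SAP |
|---|---|---|
| Discharge | Day 5 | Day 4 |
| PK return visits | Days 6, 8, 14 | Days 5, 7, 14 |
| Chemistry/hematology, in-clinic post-dose | Days 1, 2, 3, 4, 5 = 5 | Days 1, 2, 3, 4 = 4 |
| Urinalysis, in-clinic post-dose | Days 2, 3, 4, 5 = 4 | Days 2, 3, 4 = 3 |
| aPTT/PT and the six markers, in-clinic post-dose | Day 5 = 1 | Day 4 = 1 |

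Adding the Day 21 visit, the protocol has 5 + 1 = 6, 4 + 1 = 5 and 1 + 1 = 2 post-dose timepoints. How many lack a SAP counterpart depends on how visits are matched:

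- By study day, the Day 5 draw is unmatched: 1 of 6 for chemistry/hematology, 1 of 5 for urinalysis, and 1 of 2 for aPTT/PT and the markers.
- By the discharge label, the Day 4 draw is unmatched: 1 of 6 and 1 of 5. For aPTT/PT and the markers it is 0 of 2.

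Internal consistency: SAP 9.2.3 defines post-dose study day as measurement date minus dose date plus 1. So 72 h is 3 + 1 = Day 4, and 96 h is 4 + 1 = Day 5. Appendix 2 keeps a 96 h plasma sample and a 72–96 h urine interval, and SAP 16.1.2 computes cumulative 0–96 h excretion. Its urine row has no mark after Day 4. The 96 h plasma sample would fall on the day of the first return visit, which the appendix treats as a separate brief visit.

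Baseline: SAP 9.2.1 refers to Appendix 2, but the Day -1 and Day 1 pre-dose laboratory cells are the same in both schedules.

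**2. Markers**

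- Named in SAP 17.1, 17.1.3 or Appendix 3: troponin and CK-MB, 2 of 6. The other 6 − 2 = 4 (cystatin C, NGAL, UACR, testosterone) appear only in Appendix 2.
- Fold-of-limit rule carried over: 0 of 6.
- Rows in the SAP Appendix 5 toxicity table: 0 of 6 (the nearest is CPK).

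Without a fold rule or a table row, only PI grading remains. The protocol has the same fallback, but with the fold rule for these markers alongside it.

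Panel membership is not stated. Protocol 4.5 counts NGAL and cystatin C as clinical chemistry monitoring, the draw order in 11.3.1.7 pairs testosterone with biochemistry, and UACR is a urine test. Protocol Table 8 lists all four among additional tests, but it lists troponin, CK-MB and PT/aPTT there too, and the SAP still gives those a panel. Inclusion under chemistry or urinalysis is plausible, but it is not written down.

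**3. Grouping**

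| SAP table | Protocol 12.3.1.3 | SAP 17.1.3 |
|---|---|---|
| 14.3.5.1 descriptive results | cohort, visit, treatment assignment | cohort, timepoint |
| 14.3.5.2 shifts | treatment group | none stated |
| 14.3.5.3 graded toxicities | treatment group | none stated |

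The SAP's general rules bear on this. SAP 9.1.3 bases percentages on subjects exposed within a treatment, and 9.1.4 pools placebo in summary outputs. SAP 17.0 runs safety analyses cohort by cohort, which is not reconciled with 9.1.4. Protocol 12.3.1.3 contains the same tension, so that part is not a SAP change.

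**The case against.** The strongest reply is that little of this would alter a result.

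**Grouping.** A reader might infer that each cohort column mixes 6 galidesivir with 2 placebo subjects and so dilutes any effect. The documents do not support that. Such a column would contradict 9.1.4, and two of the three tables report percentages, whose denominator 9.1.3 sets per treatment. Nor is cohort-only wording peculiar to laboratory data: the overall AE summary in 17.1.1 and the demographics in 13.1 use it too. This stands. What remains is that 17.1.3 words three tables differently from the protocol.

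**Markers.** Section 17 names panels and not single analytes, and all laboratory data must be listed while Appendix 3 offers only panel listings. A reader might infer that the four markers would go unanalysed, and that does not follow. The fold rule is only sketched in the protocol, is qualified as applying where applicable, and has no cut-points. That also stands. But the protocol handed the detail to the SAP, and the SAP supplies none.

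**Schedule.** No SAP text assigns draws to Appendix 2 columns, SAP 9.1.5 leaves out only unscheduled measurements, and a Day 5 draw is scheduled in the protocol. Loss of data is therefore not shown, and every value is still listed. Even so, the summaries run by scheduled timepoint, and the only schedule in the SAP lacks one.

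**Shells.** SAP 9.5 says "TFL shells are provided with and approved as part of this SAP", and Appendix 4 says "Shells are provided in a separate document". They were not available here and may settle parts of the marker and grouping points. They would not remove the conflict inside Appendix 2 or make the 7.1 statement accurate.

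**Conclusion.** The point holds as a set of undeclared conflicts between the SAP text and the protocol in a primary-endpoint domain.

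- **Schedule:** Appendix 2 is one in-clinic day short. One of 6 chemistry/hematology and one of 5 urinalysis post-dose timepoints have no SAP counterpart under either way of matching. For coagulation and the six markers the number of timepoints is unchanged and only the day label differs.
- **Markers:** the fold-of-limit rule is absent for all six, and four of the six have no stated panel.
- **Grouping:** none of the three laboratory tables has the treatment grouping in 17.1.3 that the protocol requires. This is wording to correct.

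Two assumptions matter. The SAP says it was built on the protocol dated 11-Jan-2019, and the date of the protocol reviewed here is not visible, so part of the schedule difference could reflect versions. The clash with the SAP's own 96 h collections does not depend on that. The second assumption is that the unseen shells do not already resolve the marker and grouping points.

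The comparison does not show which discharge day is right, only that the two schedules must be reconciled. The study is descriptive with no hypothesis test, so no error rate or power is affected. The correction should be made before database lock.

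**What to change.** - Reconcile SAP Appendix 2 with the protocol version in force, so that every scheduled laboratory draw, and the 96 h plasma and 72–96 h urine collections, has a named timepoint.
- In 17.1.3, state that the laboratory summary, graded-toxicity and shift tables are presented by galidesivir dose level and pooled placebo, and align 17.0 with 9.1.4.
- Restore fold-of-limit grading for the six markers. The protocol gives no cut-points, so these need to be set in the SAP before database lock and unblinding.
- Assign cystatin C, NGAL, UACR and testosterone to a panel that is summarised with change from baseline.
- Check the shells against these changes, and record any intended departure in 7.1.
- As tidying only, delete the DMID Grade 4 shift category, since Appendix 5 stops at Grade 3.

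The cost is SAP text and appendix edits, with shell edits only where the shells share the gaps. No visit, sample or subject is added.

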4.5. Benefit-Risk Analysis

Galidesivir is a parenterally available small molecule nucleoside analog inhibitor of viral RNA polymerase activity, mediated through non-obligate RNA chain termination. Nucleoside analogs

have a proven mode of action in the treatment of multiple human viral infections. As a class, some nucleoside analogs have been associated with serious adverse reactions, including peripheral neuropathy, myopathy, pancreatitis, and lactic acidosis with hepatic steatosis, resulting from mitochondrial toxicity following chronic dosing (Lund, Peterson et al. 2007). There is no evidence in the literature of acute severe adverse reactions resulting from treatment with nucleoside analogs following single doses or up to 1 week of dosing.

- Toxicity studies in the cynomolgus monkey and rat have been conducted with IV infusion administration. Although C_{max} and AUC are lower following IV infusion compared with IM injection, no new findings have been identified from IV infusion toxicology studies. Therefore, the IM studies provide useful toxicological information to develop appropriate monitoring in an IV study.
- Toxicology studies in rats and monkeys summarized in the IB suggest that the primary target organs of galidesivir toxicity following IM administration in the rat were the kidney and liver, with toxicities also observed in the spleen, testes, thymus, heart, hematopoietic system, and injection sites. Target organs of systemic toxicity in the monkey were kidney, liver, lymphoid system, and injection sites. The principal target organ of systemic toxicity in rats and monkeys following IV infusion was the kidneys (Section 4.2.3). Microscopic changes in liver and kidney correlated to monitorable changes in relevant clinical chemistry analytes and were reversible. The large intestine was also a target in rats at the highest dose examined; minimal-to-mild single cell necrosis/degeneration in the cecum (with colon and rectum less frequently affected), with or without concurrent mucosa crypt epithelium hyperplasia/hypertrophy and/or mucosa inflammation. Galidesivir is compatible with human blood and does not cause hemolysis at concentration up to and including 15 mg/mL.

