10.1.3. Follow-up/Early Termination Visit

Subjects will return to the clinic on Day 21 +2 for a follow-up visit. If a subject terminates from the study at any point prior to the scheduled follow-up visit, the assessments listed below should be performed at that time.

The following procedures will be performed at the follow-up visit:

- Safety laboratory assessments (clinical chemistry, aPTT/PT, hematology, coagulation)
- Blood drawn for testosterone, troponin I, CK-MB, NGAL, Cystatin C
- Urinalysis
- Determine UACR
- 12-lead ECG
- Vital Signs (blood pressure and heart rate)
- Physical examination
- Review of AEs and concomitant medications
- Blood sample collected for analysis of galidesivir concentrations
- Urine pregnancy test for all women

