12.3.1.3. Analysis of Safety Variables

AEs will be mapped to a Medical Dictionary for Regulatory Activities (MedDRA) preferred term (PT) and system organ classification (SOC). Any event reported on the subject's study record that occurs on or after the initiation of study drug is defined as treatment emergent. Additionally, it is assumed that an AE that is reported to have started on Day 1 of a given treatment period without an associated onset time may have occurred after the initiation of study drug. Hence, AEs occurring on Day 1 with no associated onset time will be assumed to be treatment emergent. The occurrence of TEAEs will be summarized by cohort and treatment assignment using MedDRA PTs, SOCs, and severity. Separate summaries of treatment-emergent SAEs and AEs considered to be related to study drug will be generated. All AEs will be listed for individual subjects showing both verbatim and preferred terms.

Descriptive summaries of vital signs, ECG parameters (12 lead and telemetry), ECHOs, and clinical laboratory results will be presented separately for each cohort by study visit and treatment assignment. Laboratory abnormalities will be graded according to the modified DMID criteria ([APPENDIX A](#)).

Any graded abnormality that occurs following the initiation of study drug and represents at least one grade increase from the baseline assessment is defined as treatment emergent. The number and percentage of subjects experiencing treatment-emergent graded toxicities will be summarized by treatment group. Laboratory toxicity shifts from baseline to post-baseline assessments will be summarized by treatment group.

PE results will be presented in listings. Changes in PE results that are AEs will be reported in AE tables.

Concomitant medications will be coded using the World Health Organization (WHO) Dictionary. These data will be summarized by cohort and treatment assignment.

Subjects receiving placebo will be pooled and reported together across cohorts.

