Eosinophils - cell/mm 	15-500 cells/uL		500 – 750	751 – 1600	>1600
Platelets Decreased - cell/mm 	140,000 – 400,000/ uL		130,000 – 140,000	110,000 – 129,999	<110,000
PT – seconds (prothrombin time)	9.0-11.5 seconds		> ULN-14.4	14.5 – 15.7	>15.7
PTT – seconds (partial thromboplastin time)	22-34 sec		>ULN-34.1	34.2– 42.0	>42.0
Fibrinogen increase - mg/dL	175-425 mg/dL		>ULN – 425	426 – 525	>525
Fibrinogen decrease - mg/dL	175-425 mg/dL		<LLN – 175	160 – 174	<160
Urine *			Mild (Grade 1)	Moderate (Grade 2)	Severe (Grade 3)
Protein			1+	2+	>2+
Glucose			1+	2+	>2+
Blood (microscopic) - red blood cells per high power field (rbc/hpf)			5-10	11-50	> 50 and/or gross blood
	* The laboratory values provided in the tables serve as guidelines and are dependent upon institutional normal parameters.				
	* Institutional normal reference ranges should be provided to demonstrate that they are appropriate.				
	** Reference ranges are from Quest Diagnostics. Any age range that is not specified is 18Y – 133Y				

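### The SAP's laboratory shift table covers only continuous values from baseline to follow-up, which is narrower than Protocol 12.3.1.3, inconsistent with SAP 9.1.5 and not declared as a change

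*SAP*

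**What the plan says.** Protocol 12.3.1.3 sets the rule: "Laboratory toxicity shifts from baseline to post-baseline assessments will be summarized by treatment group". It names no single visit and does not restrict the type of result.

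SAP 17.1.3 replaces this with: "A shift table describing the change in continuous clinical laboratory values from baseline to follow-up (number and percentage of subjects) will also be provided". The shift sentence does not mention treatment group. It continues: "The following categories will be used: Normal, DMID Grade 1, DMID Grade 2, DMID Grade 3, DMID Grade 4". SAP 7.1 then states: "There are no changes from the protocol".

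Both documents use follow-up as the name of one visit. Protocol 10.1.3 says "Subjects will return to the clinic on Day 21 +2 for a follow-up visit", and the notes to the SAP's schedule (Appendix 2) say "A plasma PK sample will also be collected at the follow-up visit on Day 21". In both schedules the last column is the follow-up or early-termination visit.

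Two other parts of the SAP bear on the point. Section 9.1.5 says that, for shift and worst-outcome tables, unscheduled values falling between one timepoint and the next scheduled one are counted. Section 17.1.3 also asks for counts of treatment-emergent graded toxicities (Table 14.3.5.3), descriptive summaries of continuous results by timepoint (Table 14.3.5.1) and a listing of out-of-range values (Table 14.3.4).

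**The concern.** Laboratory abnormalities are part of the primary endpoint (Protocol 6.1). Protocol 4.5 names the kidneys as the principal target organ of systemic toxicity in animals after IV infusion, and adds: "Microscopic changes in liver and kidney correlated to monitorable changes in relevant clinical chemistry analytes and were reversible". In a single-dose study, the effect to look for is therefore an early change that recovers. A table comparing baseline only with Day 21 is poorly placed to show it.

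The restriction to continuous values has a similar effect. Dipstick urine protein is a renal marker and a screening inclusion test (Protocol Table 6). Appendix 5 grades it on an ordinal scale, so it falls outside the table as worded.

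SAP 3.0 says that the SAP supersedes the protocol's statistical section and identifies substantial differences. A programmer would therefore follow 17.1.3, and nothing would tell the reader of the report that the protocol's table had been narrowed.

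**Working it through.** The plan states no figure on this point, so there is none to reproduce. The check has four steps.

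**1. Share of post-dose assessments used if follow-up means Day 21**

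| Schedule | Chemistry/hematology | Urinalysis |
|---|---|---|
| Protocol Table 5 | Day 1 post-dose, Days 2, 3, 4, 5, 21: 1 of 6 | Days 2, 3, 4, 5, 21: 1 of 5 |
| SAP Appendix 2 | Day 1 post-dose, Days 2, 3, 4, 21: 1 of 5 | Days 2, 3, 4, 21: 1 of 4 |

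The two schedules differ because SAP Appendix 2 has discharge on Day 4 and Protocol Table 5 has it on Day 5.

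**2. What the table would display**

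The values below are invented to show the mechanism. Grades are from Appendix 5, for a man aged 20 to 49:
- Creatinine (mg/dL): normal to 1.35, Grade 1 to 1.45, Grade 2 to 1.65, Grade 3 above 1.65.
- ALT (U/L): normal to 46, Grade 1 to 101, Grade 2 from 102 to 171, Grade 3 above 171.

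| Analyte | Baseline | Days 1 to 5 | Day 21 | Shift to Day 21 | Shift to worst grade |
|---|---|---|---|---|---|
| Creatinine | 1.00 | 1.1, 1.3, 1.7, 1.5, 1.3 | 1.05 | Normal to Normal | Normal to Grade 3 |
| ALT | 30 | 32, 60, 110, 120, 90 | 35 | Normal to Normal | Normal to Grade 2 |

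Both profiles are treatment-emergent under Protocol 12.3.1.3 (a rise of at least one grade), so both would count in Table 14.3.5.3. A by-timepoint shift table would also show them, creatinine as Grade 3 on Day 3 and ALT as Grade 2 on Days 3 and 4.

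Suppose there were also an unscheduled ALT of 60 on Day 8. Under SAP 9.1.5 it would fall in the Day 21 window, and the Day 21 shift would become Normal to Grade 1. That is still below the Grade 2 peak.

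**3. Analytes outside the word continuous**

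Appendix 5 grades urine protein and urine glucose as 1+, 2+ and above 2+. These are ordinal, so they are excluded from the shift table. They are equally outside Table 14.3.5.1, which is also confined to continuous results. Their remaining outputs are Table 14.3.5.3 and the listings. Microscopic blood is graded on a count ("Blood (microscopic) - red blood cells per high power field (rbc/hpf") and could be handled as numeric. Protocol Table 8 makes microscopy conditional on an abnormal dipstick and on the investigator's discretion. Whether it would be dropped cannot be settled from the documents.

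**4. Categories**

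Appendix 5 defines Grades 1, 2 and 3 only, so no laboratory value can be assigned to the Grade 4 category from it.

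**The case against.** The strongest reply is that this is loose drafting and not a fixed Day 21 rule. Section 17.1.3 says follow-up without naming a day. Protocol 11.4 also uses the word for a period. The title of Table 14.3.5.2 names no end visit, and SAP 9.1.5 speaks of each scheduled timepoint. The table shells are approved with the SAP (9.5) but held in a separate document, and the shell may settle the matter. All of this stands, so Day 21 is the natural reading but not the only one. It does not remove the point. Section 9.1.5 says which unscheduled values count and never sets the table's end point, so two programmers could build different tables from the same text.

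Four stronger inferences are tempting but unsupported:

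- *Transient abnormalities would be hidden.* They would not. Table 14.3.5.3 counts treatment-emergent grades without restriction to Day 21 or to continuous results, and Table 14.3.4 lists abnormal values. An unscheduled value or an early-termination visit could also bring an abnormality into the shift table itself.
- *The shift table would contradict Table 14.3.5.3.* A Day 21 shift describes recovery, whereas an any-time count describes occurrence. The two can look inconsistent side by side, but they answer different questions.
- *The protocol requires worst post-baseline grade.* It does not use the word worst. A by-timepoint shift table would also satisfy it.
- *The drug's half-life shows that abnormalities would be gone by Day 21.* Residual drug concentration does not say whether creatinine or ALT has returned to normal, so it does not measure the defect.

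**Conclusion.** The point holds as an undeclared narrowing and an internal inconsistency in one primary-endpoint safety table. On the natural reading, the table uses 1 of 6 scheduled post-dose chemistry/hematology assessments (1 of 5 in the SAP's schedule). It would generally show Normal to Normal for a grade that appears on Days 1 to 5 and resolves by Day 21, and it omits graded dipstick protein and glucose. The Grade 4 category is a plain specification error, although its column would simply be empty.

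The loss is the cross-tabulation of baseline grade against post-baseline grade by treatment. The events themselves remain in other outputs, and no inferential result depends on the table. Severity is minor to moderate. This rests on two assumptions: that follow-up means the Day 21 visit, and that the unseen shell follows the text of 17.1.3. If the shell already shows shifts at each timepoint for all graded analytes, what remains is a wording correction.

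**What to change.** In SAP 17.1.3, replace the shift sentence with one along these lines: *A table will show the shift from baseline grade to the worst post-baseline grade, using all scheduled and unscheduled values after the start of infusion through Day 21, by dose group and pooled placebo, for every analyte graded in Appendix 5 (including urine protein, glucose and microscopic blood where recorded), with low and high directions shown separately.* A by-timepoint shift is an acceptable alternative under the protocol.

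In the same edit:
- Align the wording with SAP 9.1.5 and Protocol 12.3.1.3.
- Delete the Grade 4 category.
- Carry the protocol's definition of a treatment-emergent laboratory grade into 17.1.3, since Table 14.3.5.3 depends on it.
- Optionally keep a baseline-to-Day 21 panel, labelled as recovery.

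If the sponsor prefers the narrower table, SAP 7.1 should declare it. The cost is a wording change and one table shell. No new data are needed, and the only drawback is a slightly longer table.
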